2.3. Secondary Efficacy Objectives and Endpoints

The Secondary Efficacy Objectives of the study are:

- Change from baseline in the symptoms of Parkinson's disease
- Change from baseline in cognition
- Change from baseline in psychosis

[figure not shown]
Secondary Efficacy Endpoints will include the following:

- Change from baseline in the MDS-UPDRS Parts 1-3 score at the end of the 12-week fixed dose period. Baseline is defined as the MDS-UPDRS score at the screening Visit of this roll-over study.
- Change from baseline in cognition will be assessed by MMSE scores at the end of the 12-week fixed dose period. Baseline is defined as the MMSE score at the screening Visit of this roll-over study.
- Change from baseline in psychosis as assessed by the SAPS-PD at the end of the 12-week fixed dose period. Baseline is defined as the SAPS-PD score at the screening Visit of this study.

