3.1. Pre-Screening Planning

Subjects who wish to continue taking ENT-01 after completing the ENT-01-030 study may “roll over” into this study. They can do this on the same day as their final study visit (Visit 6) for ENT-01-030, but they are not required to do so. Keep in mind the following to help with planning for “roll over” subjects:

- Informed Consent may be obtained before ENT-01-030 Visit 6 or Visit 1 of this study. Doing so would allow the subject to discontinue or refrain from the use of any prohibited medications listed in [Section 7](#) prior to the visit, potentially allowing them to take the ENT-01 study medication earlier.
- There is no limit on the amount of time between completing ENT-01-030 and being able to screen for this study.
- If the subject “rolls over” within 14 days of ENT-01-030 Visit 6, then any procedures common to both studies do not need to be repeated. See [Appendix 2: Schedule of Events](#) and the individual visit descriptions below.
- Subjects may retain their ENT-01-030 diary device for use in this study.
- If the subject started or restarted any medications listed in [Section 7](#) of this protocol before their ENT-01-030 Visit 6, they will need to discontinue them for 14 days before starting to take the ENT-01 study medication. This may affect the timing of Visit 2, depending on how long it takes them to reach a fixed dose.
- If a subject is taking levodopa and has fluctuations but does not “roll over” on the same day as their ENT-01-030 Visit 6, remind them about levodopa dose timing for the MDS-UPDRS.

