3.2. Visit 1: Screening and Dose Escalation Period (Day -20 to Day 1)

Reminders

- Once consented and eligibility is confirmed, subjects with fluctuations and prescribed levodopa should take their daily levodopa dose so that they are in an ON state when the MDS-UPDRS is administered. For most subjects, this would be approximately 60 minutes after taking levodopa.
- Subjects must have discontinued and refrain from using any laxatives, constipation medications, and other medications as specified in [Section 7](#) for 14 days prior to starting ENT-01 dosing. (These “washout” days are not counted in the schedule, as described below.)

Perform the assessments and procedures as listed in Appendix 2: Schedule of Events:

- Informed consent
- Inclusion/Exclusion Criteria
- Demographics/Medical History
- Complete Physical Exam
- Weight (Height from ENT-01-030 will be used, so it is not required to be recorded)
- Orthostatic Vital Signs: Vital signs will include supine blood pressure and heart rate, sitting or standing blood pressure and heart rate, respiratory rate, and body temperature. Supine measurements will be taken after the subject has been in the supine position for at least 5 minutes. Sitting or standing measurements will be taken within 5 minutes of the subject sitting or standing from the supine position.
- 12-lead EKG
- Labs (chemistry, hematology, and urinalysis): as defined in [Appendix 1: Laboratory Tests](#).
- Pregnancy Testing – For women of child-bearing potential, this is done on-site with the urine pregnancy kit (UPT) provided. If the on-site UPT is positive, then a serum pregnancy test will be done. For post-menopausal women less than 60 years of age, a serum FSH will be done at the screening visit only.
- Instruct subject to refrain from using or discontinue the use of any laxatives, constipation medications, and other medications as specified in [Section 7](#) for 14 days prior to starting ENT-01 dosing. Determine the date ENT-01 dosing should begin and provide to the subject. (Although Visit 1 is listed as Day -20, that is more of a rough estimate for schedule planning. Most subjects should get to their fixed dose before 20 days; at that point Day 1 for that subject is set and their remaining visits are scheduled based on Day 1.)

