3.4. Visit 3: 6th week of FDP (Day 43, +/- 3 days)

Perform the assessments and procedures as listed in [Appendix 2: Schedule of Events](#):

- Brief Physical Exam (review of body systems as indicated)
- Weight
- Orthostatic Vital Signs: Vital signs will include supine blood pressure and heart rate, sitting or standing blood pressure and heart rate, respiratory rate, and body temperature. Supine measurements will be taken after the subject has been in the supine position for at least 5 minutes. Sitting or standing measurements will be taken within 5 minutes of the subject sitting or standing from the supine position.
- 12-lead EKG
- Labs (chemistry, hematology, urinalysis, pregnancy): as defined in [Appendix 1: Laboratory Tests](#).
- IP Collection and Accountability
- Dispense Rescue Medication, as needed. Subjects continue appropriate use of rescue medication, ensuring adequate bowel movements every 3 days.
- Dispense ENT-01 for 6 weeks of dosing with instructions regarding dosing.
- Re-educate subject with respect to stool diary daily entries.
- Assess for Adverse Events (new, ongoing, since last visit, etc.)
- Review Concomitant Medications/Therapies (current, since last visit, etc.)
- MDS-UPDRS – Only Parts I, II, and III of the scale will be rated, assessed by personnel certified in the MDS-UPDRS. Subjects with fluctuations and prescribed levodopa should be assessed when in an ON state. Non-fluctuating subjects and subjects not on levodopa can be assessed at any point during the visit.
- SAPS-PD (subjects who scored > 0 on the SAPS-PD at screening)

3.5. Visit 4: 12th week of FDP, Start of WOP, ET (Day 85, +/- 3 days)

Perform the assessments and procedures as listed in [Appendix 2: Schedule of Events](#):

- Brief Physical Exam (review of body systems as indicated)
- Weight
- Orthostatic Vital Signs: Vital signs will include supine blood pressure and heart rate, sitting or standing blood pressure and heart rate, respiratory rate, and body temperature. Supine measurements will be taken after the subject has been in the supine position for at least 5 minutes. Sitting or standing measurements will be taken within 5 minutes of the subject sitting or standing from the supine position.
- 12-lead EKG
- Labs (chemistry, hematology, urinalysis, pregnancy): as defined in [Appendix 1: Laboratory Tests](#).
- IP Collection and Accountability
- Reinstate all discontinued medications, antacids, proton pump inhibitors and laxatives.

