7. CONCOMITANT AND PROHIBITED MEDICATIONS AND THERAPIES

Categories of medications are listed below. Enterin will provide investigative sites with detailed listings of specific medications. All medications shall be reviewed and approved or disapproved by the investigator on a case-by-case basis.

Prohibited Medications to be discontinued at Screening (V1) and restarted during the wash-out period (V4):

- All oral laxatives, osmotic laxatives, pro-kinetic laxatives, stimulant laxatives, bulking agents, stool softeners, and suppositories, except for rescue medications used as directed in this protocol.
- Antacids
- Opiates
- Proton pump inhibitors
- Certain antipsychotics that worsen symptoms of Parkinson's disease.
- Certain antidepressants that worsen symptoms of Parkinson's disease.

Concomitant Medications permitted at stable doses

- Anticholinergics
- Antihistamines and anti-histaminergic agents
- Catechol-O-methyltransferase COMT inhibitors
- Certain antipsychotics
- Certain antidepressants, including tricyclic and quadricyclic antidepressants
- Dopamine agonists and amantadine (if on a stable dose for at least 2 weeks preceding the study).
- Certain dopamine reuptake inhibitors
- Dopamine metabolism inhibitors
- Dopaminergic compounds
- Selective serotonin reuptake inhibitors (SSRI)
- Serotonin and norepinephrine reuptake inhibitors (SNRI)

Permitted Therapies

- Deep brain stimulation, if present for more than 6 months and at stable stimulation parameters.

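### For subjects still on Section 7 drugs when the MDS-UPDRS, MMSE and SAPS-PD baselines are rated, the week-12 change mixes drug withdrawal with any ENT-01 effect

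*Combined protocol and SAP*

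**What the plan says.** **Baseline.** Section 2.3 defines all three secondary baselines by the same visit: "Baseline is defined as the MDS-UPDRS score at the screening Visit of this roll-over study"; "Baseline is defined as the MMSE score at the screening Visit of this roll-over study"; "Baseline is defined as the SAPS-PD score at the screening Visit of this study".

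**Withdrawal.** The list in Section 7 is headed "Prohibited Medications to be discontinued at Screening (V1) and restarted during the wash-out period (V4"). One entry reads "Certain antipsychotics that worsen symptoms of Parkinson's disease"; a parallel entry covers certain antidepressants, and opiates are also listed. Other antipsychotics and antidepressants may continue at stable doses. Section 3 gives the same off-drug window, Visit 1 to Visit 4. Exclusion criterion 3 (Section 5) adds clonazepam.

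**Timing at Visit 1.** Section 3.2 puts the three ratings and the instruction to stop the Section 7 drugs in the same visit. The 14 days are counted back from the first ENT-01 dose, not from the rating, and "These “washout” days are not counted in the schedule, as described below". Dosing starts the next morning or on a later date given to the subject.

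**Roll-over provisions.** Section 3.1 lets consent be taken early, so that a subject can be off these drugs before the visit, but does not require it. For roll-over within 14 days of the last KARMET visit (Visit 6), "then any procedures common to both studies do not need to be repeated". The same section foresees subjects who restarted listed drugs before KARMET Visit 6.

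**End of dosing and analysis.** Visit 4 (Section 3.5) includes the step "Reinstate all discontinued medications, antacids, proton pump inhibitors and laxatives". Section 11.5 analyses the secondary endpoints by the primary method, states no adjustment for withdrawn drugs, and promises sensitivity analyses only for the primary endpoint.

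**The concern.** A baseline should describe the subject just before the study drug, under the conditions that hold during treatment. Here a subject can be rated while taking a drug that the protocol says aggravates the disease being rated, then stop it, then start ENT-01. The week-12 rating follows both changes. Because the study has one arm, no comparator group undergoes the withdrawal alone.

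The protocol accepts elsewhere that drug state affects these scores: fluctuating subjects on levodopa are to be rated in the ON state. It does not apply the same care to the drugs it orders stopped.

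At stake is the interpretation of the motor, cognition and psychosis endpoints for the affected subjects. The primary bowel-movement endpoint takes its baseline from KARMET and is not touched by this point.

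**Working it through.** **1. Order of events.** This is the path of a subject on a listed drug at Visit 1 who did not consent early (Sections 3.2 to 3.6, Section 7, Appendix 2):

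| Time | Listed drug | ENT-01 | MDS-UPDRS | SAPS-PD | MMSE |
|---|---|---|---|---|---|
| Visit 1 | on; told to stop | none | baseline | baseline | baseline |
| 14-day withdrawal | off | none | none | none | none |
| Escalation, up to 20 days | off | rising | none | none | none |
| Visit 2, Day 1 | off | fixed | rated | if Visit 1 score > 0 | none |
| Visit 3, Day 43 | off | fixed | rated | if Visit 1 score > 0 | none |
| Visit 4, Day 85 | off, then reinstated | ends | endpoint | endpoint if Visit 1 score > 0 | endpoint |
| Visit 5, Day 127 | may be back on | none | rated | if Visit 1 score > 0 | none |

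The first rating after withdrawal is Visit 2, already on ENT-01; for MMSE it is Visit 4. On the nominal schedule the subject has been off the drug at Visit 4 for 14 + 84 = 98 days plus escalation time, so up to 14 + 20 + 84 = 118 days.

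**2. Who is affected.** Only subjects on such a drug at the rating used as baseline who stop it afterwards. Subjects who never took one, or were already off it through early consent, are unaffected. The documents give no count.

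**3. Direction.** For the named antipsychotics and antidepressants, the protocol's own description implies that stopping them could look like improvement on MDS-UPDRS. Nothing is said for MMSE. For SAPS-PD, stopping an antipsychotic could move the score the other way. In addition, a subject who scores 0 on SAPS-PD at Visit 1 while on an antipsychotic is not re-rated, so a change after withdrawal would not be seen on that scale.

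**4. Size.** The plan's only sample-size figure concerns safety, and it reproduces: 1 - 0.95^50 = 0.923, stated as 92%. Expected completers are 50 x (1 - 0.20) = 40, as Section 4 states. Neither depends on the secondary baselines. No SD, withdrawal effect or share of users is given, so every share and effect below is an assumption.

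Bias in the mean change = f x d, where f is the share withdrawn after the baseline rating and d is the mean withdrawal effect. In MDS-UPDRS points:

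- 0.05 x 2 = 0.1
- 0.10 x 4 = 0.4
- 0.30 x 6 = 1.8

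In units of the SD of change, consider n = 40, no true ENT-01 effect and a two-sided 5% one-sample z test. The chance of a significant result is 1 - Φ(1.96 - f·d·√n) + Φ(-1.96 - f·d·√n):

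| f | d (SD) | Bias (SD) | Chance of significance |
|---|---|---|---|
| 0 | any | 0 | 5.0% |
| 10% | 0.25 | 0.025 | 5.3% |
| 20% | 0.5 | 0.10 | 9.7% |
| 30% | 0.5 | 0.15 | 15.8% |
| 50% | 1.0 | 0.50 | 88.5% |

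For the third row, 0.10 x √40 = 0.632, giving 0.092 + 0.005 = 0.097. The z test is a simplification of the planned mixed model. The last row is an extreme, included to show the range.

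**5. Price of leaving flagged subjects out.** The standard error grows by √(40/n remaining). With 10% flagged it is √(40/36) = 1.05; with 20%, √(40/32) = 1.12; with 30%, √(40/28) = 1.20.

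**The case against.** The strongest reply is that the affected group may be small or empty. Early consent exists so that drugs can be stopped before the visit, only certain antipsychotics and antidepressants are prohibited, and the investigator reviews medication case by case. These are also secondary endpoints of an unblinded, single-arm safety study, which would not isolate a drug effect even with a perfect baseline. Both points stand and limit the weight of the concern. They do not remove it: early consent is optional, and the baseline definition does not depend on it.

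Visit 2 offers a partial check, since MDS-UPDRS is rated there after withdrawal. But that rating is on ENT-01, so the Visit 2 to Visit 4 change omits any effect gained during escalation. It does not help MMSE.

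Several stronger readings are tempting, and the documents do not support them:

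- A reader might infer that opiates and clonazepam are also said to worsen Parkinson's symptoms. That description is attached only to certain antipsychotics and antidepressants. The other two matter only as drugs that change between the ratings.
- A reader might infer that all three KARMET scores can be carried over. Section 3.1 suggests that KARMET Visit 6 includes MDS-UPDRS; for MMSE and SAPS-PD this is not shown.
- A reader might infer that reinstating drugs at Visit 4 biases an endpoint. All three secondary endpoints end at week 12. The overlap affects only how Visit 5 scores are read.
- A reader might conclude that withdrawal should be moved ahead of Visit 1. That would change the timing of clinical management, placing it before the eligibility checks, labs and rescue supply of that visit. It could also add a consent contact or delay dosing. The statistical problem does not require it.

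**Conclusion.** The concern holds for a defined subgroup: subjects on a listed drug at the rating used as baseline who stop it afterwards. For them the week-12 change in MDS-UPDRS, MMSE and SAPS-PD contains a withdrawal component that the design cannot separate from ENT-01. The likely direction is favourable for MDS-UPDRS, unstated for MMSE and possibly unfavourable for SAPS-PD.

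The size cannot be computed from the documents. The range of 0.1 to 1.8 MDS-UPDRS points, and a chance of significance of 9.7% against a nominal 5% at a 20% share and a 0.5 SD shift, rest wholly on assumed inputs. If no subject meets the condition, the bias is zero. A reader might infer that the secondary results are invalid for everyone, or biased towards ENT-01 on every scale; neither follows. The point merits a short change to the analysis plan and does not call the safety or primary efficacy analysis into question.

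**What to change.** 1. **Flag and repeat (Sections 2.3 and 11.5).** From the medication review, flag each subject who was on a Section 7 antipsychotic, antidepressant or opiate, or on clonazepam, at the rating used as baseline and stopped it afterwards. Repeat the three secondary analyses without them and report both results with the number flagged. If the results differ, do not attribute the change to ENT-01 alone. A difference may also reflect who takes these drugs, and agreement is weak evidence when few are flagged.
2. **Carried-over scores (Section 3.1).** Where a subject was on such a drug at KARMET Visit 6 but has completed the withdrawal by Visit 1, rate the scales at Visit 1 instead of carrying over the KARMET score. The waiver and the withdrawal are both 14 days, so this should reach few subjects; the flag in step 1 covers the rest.
3. **Visit 5.** Present any Visit 5 scores by whether such a drug was reinstated at Visit 4, as description only.

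The sponsor should also reconcile the baseline definition in Section 2.3 with the withdrawal timing in Sections 3, 3.1, 3.2 and 7. No change is proposed to which drugs are stopped or restarted, or when.

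**Cost.** Medications are already reviewed at every visit, so step 1 needs no new procedure. The repeat analysis loses precision: a standard error about 5% to 20% larger if 10% to 30% of 40 completers are flagged. A few roll-over subjects repeat scales they could have skipped. The repeat analysis does not recover SAPS-PD ratings that were never taken in subjects who scored 0 at Visit 1; that should be stated as a limitation.

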3. STUDY DESCRIPTION

The purpose of this Study is to obtain safety data and stool diary data out to approximately 14 weeks (approximately 2 weeks of dose escalation plus 12 weeks of fixed dosing, see [Figure 1](#) below.) All subjects who participated in the randomized KARMET trial (ENT-01-030, Stage 2 Extension subjects) and who are interested in participating in this open label safety roll-over study will be offered participation. Subjects from KARMET Stage 1 (non-randomized) are not eligible to participate in this roll-over study. There is no restriction on the time lag between the subject's prior participation in ENT-01-030 and eligibility to enroll in this study, and subjects may enroll in this study the same day as completing the final study visit (Visit 6) of ENT-01-030.

Figure 1: Illustration of Study Visits

Approximately 50 subjects will be entered at up to 20 sites in the US, assuming 75% of patients randomized to ENT-01 and 50% of patients randomized to placebo choose to participate. Each subject will have 5 visits to the clinic in person (under exceptional circumstances some of these may have to be conducted via Telemedicine): Visit 1/Screening or dosing initiation; Visit 2/Beginning of Fixed Dose period (FDP); Visit 3/End of 6 weeks of FDP; Visit 4/End of 12 weeks of FDP; Visit 5/end of 6 weeks of wash out period (WOP)/End of study. It is anticipated that the duration of study participation for each subject will be approximately 20 weeks, as it is anticipated that the majority of subjects will require less than 20 days to reach their fixed dose.

Subjects will discontinue opiates and all laxatives, bulking agents, stool softeners, suppositories, proton pump inhibitors, antacids, and certain antipsychotics and antidepressants from Visit 1/Screening until Visit 4/End of 12 weeks of FDP. Where on stable doses, subjects may continue the use of antihistamines and anti-histaminergic agents, anti-cholinergics, COMT inhibitors, dopamine agonists, amantadine, and certain anti-psychotic and anti-depressant medications. (See [Section 7](#) Concomitant and Prohibited Medications and Therapies.)

Subjects will keep daily electronic stool diaries and will record information concerning stools immediately after each bowel movement, including stool frequency, consistency, ease of evacuation, completeness, and the use of rescue medication. Site staff will monitor these entries regularly to ensure subjects are not at risk of becoming impacted and are using rescue medication appropriately. Site staff will contact subjects if the web-based questionnaires are not being completed on a daily basis or if there are any safety concerns.

Each subject will be started on a pre-defined dose based upon their baseline CSBM rate during the randomized study, then will be able to increase their dose every 2-3 days until they reach a pro-kinetic dose or the maximum dose of 250mg. This is called the Dose Escalation Period (DEP). After the subject documents 4 CSBMs over 5 consecutive days, the subject will fix at that dose for the remainder of the study. This is called the Fixed Dose Period (FDP). At the end of the FDP medication will be discontinued and a 6-week wash-out period (WOP) will follow. Daily stool e-diary will be entered throughout the dosing period.

Rescue medications (including oral Bisacodyl, suppositories, and enemas,) will be provided to subjects and will be initiated in the evening of the third day if a subject has had no bowel movement for three consecutive days.

Study medication will be taken on an empty stomach first thing in the morning with 8 oz water and no food will be allowed for 60 minutes. Subjects prescribed levodopa should wait at least 30 minutes between taking levodopa and study medication. Tea and coffee with/without milk/sugar and orange juice (without pulp) are permitted. Plain yoghurt can be added if the patient experiences repeated nausea.

Symptoms of Parkinson's disease will be assessed using the Unified Parkinson's disease Rating Scale (MDS-UPDRS, Parts I-III) by certified raters and patients with fluctuations and prescribed levodopa will be assessed during "ON" states, approximately one hour after levodopa intake.

Subjects who prematurely discontinue study drug for any reason will be asked to have an Early Termination (ET) visit within 3 days following the last study drug dose. If a subject discontinues study drug during a scheduled visit, then the Early Termination visit will be conducted at that time. (Early Termination visit assessments are the same as Visit 4.)

3.1. Pre-Screening Planning

Subjects who wish to continue taking ENT-01 after completing the ENT-01-030 study may “roll over” into this study. They can do this on the same day as their final study visit (Visit 6) for ENT-01-030, but they are not required to do so. Keep in mind the following to help with planning for “roll over” subjects:

- Informed Consent may be obtained before ENT-01-030 Visit 6 or Visit 1 of this study. Doing so would allow the subject to discontinue or refrain from the use of any prohibited medications listed in [Section 7](#) prior to the visit, potentially allowing them to take the ENT-01 study medication earlier.
- There is no limit on the amount of time between completing ENT-01-030 and being able to screen for this study.
- If the subject “rolls over” within 14 days of ENT-01-030 Visit 6, then any procedures common to both studies do not need to be repeated. See [Appendix 2: Schedule of Events](#) and the individual visit descriptions below.
- Subjects may retain their ENT-01-030 diary device for use in this study.
- If the subject started or restarted any medications listed in [Section 7](#) of this protocol before their ENT-01-030 Visit 6, they will need to discontinue them for 14 days before starting to take the ENT-01 study medication. This may affect the timing of Visit 2, depending on how long it takes them to reach a fixed dose.
- If a subject is taking levodopa and has fluctuations but does not “roll over” on the same day as their ENT-01-030 Visit 6, remind them about levodopa dose timing for the MDS-UPDRS.

